3.3. EXPLORATORY ANALYSIS

Exploratory analysis will be conducted as deemed appropriate. Exploratory analysis will include the estimation of significant hypotensive (vasovagal/hypovolemia) AE occurring during the plasmapheresis procedure at first donation. For this endpoint, every subject will only contribute their first donation to the analysis. Modeling framework outlined in the primary analysis section will be used.

Logistic regression and/or advanced CI estimation methods for binary data will be used to estimate the proportion of donors who experience at least one significant hypotensive (vasovagal/hypovolemia) AE occurring during any of his or her plasmapheresis procedures.

Continuous and discrete modeling techniques will be used whenever applicable. Distribution summaries will be presented through summary tables and visualization methods. Further versions of the document will outline more details related to the exploratory analysis.

Sensitivity analysis may be conducted using a Modified ITT (MITT) and the per-protocol data sets in order to assess the robustness of the findings. Furthermore, to test the sensitivity of the

Statistical Analysis Plan Version: 1.0 Date: 26-Apr-2020

results to alternative modelling approach for model selection assumptions, primary and secondary analyses may be conducted using different statistical modeling (including different covariate structure for mixed effect model), different statistical tests and different methods for estimating CIs.

Analysis of key risk indicators, including but not limited to, device performance metrics, drop-out rates, assigned versus actual randomization, adverse event reporting, enrollment, subgroup imbalances, compliance to the protocol, and repeat donation frequencies will also be included in exploratory analysis.

Estimates of the incidence rate of 1.1 (Prefaint, No LOC (Minor)) hypotensive (vasovagal/hypovolemia) adverse events according to the plasma center adverse event reporting system, based on the IQPP definitions, along with their 95% CIs will be reported separately per experimental and control arms. Estimation will be conducted using Agresti-Coull method (Agresti, 1998). Modeling framework outlined in the primary analysis section may be used to statistically compare incidence rates of 1.1 (Prefaint, No LOC (Minor)) hypotensive (vasovagal/hypovolemia) adverse events between the two study arms. Similar statistical analysis and visualizations will be performed for total AEs by a study arm. The adverse event rates will statistically be compared between the two study arms by testing the null hypothesis of equal AE rates.

3.4. SUBGROUP ANALYSIS

Subgroup analysis will compare AE rates by groups in the subpopulations defined by the following variables:

- First-time donor status (First-time vs Repeat donors);
- Weight (subjects having Weight > 130lbs vs Weight \leq 130lbs);

Statistical Analysis Plan Version: 1.0 Date: 26-Apr-2020

- BMI (subjects having BMI > 30 vs BMI \leq 30);
- Gender (Males vs Females).

Subgroup analysis may not be powered enough to detect statistically significant differences in AE rates. This may occur when the proportion of the mentioned subgroup in the whole sample is small.

3.4.1. SUBGROUP ANALYSIS DEFINED BY THE FIRST-TIME DONOR STATUS

First-time donors are defined as those who have never undergone plasmapheresis prior to the study. This status will be collected as combination of the donation site historic records and self-reporting by study subjects. This information will be collected prior to randomization as follows: If the donor previously donated at the clinical site then he/she will be automatically in the repeat donor group. If no record of prior donation exists at the site, then donor will self-report the first-time donor status.

There will be two separate analyses for these subgroups performed as follows:

- *Analysis one*: Incidence rates of significant hypotensive (vasovagal/hypovolemia) AE will be compared between the experimental and control arms separately in the first-time and repeat donors, using the data from the first donations only.
- *Analysis two*: Incidence rates of significant hypotensive (vasovagal/hypovolemia) AE will be compared between the experimental and control arms separately in the first-time and repeat donors, using the data from entire ITT dataset (i.e. all donation).

ClinStatDevice

Statistical Analysis Plan Version: 1.0 Date: 26-Apr-2020

For analyses one and two estimates of significant hypotensive (vasovagal/hypovolemia) AE incidence rates along with their 95% CIs will be reported for all the subgroups. Estimation will be conducted using Agresti-Coull method (Agresti, 1998). Sensitivity analysis will be conducted using exact method based on a binomial distribution, and Wald method with or without continuity correction. If data allow, additional model based analysis will be performed with the approach outlined in the primary analysis section with introduction of additional categorical covariate representing the first-time donor status (first-time donor=0, repeat donor=1). The coefficient estimate associated with this covariate will be reported along with its 95% CI.

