3.1.1. STATISTICAL ANALYSIS METHOD

Given the nature of the data where donors contribute multiple data samples (donations), Generalized Estimation Equations Logistic Regression (GEE Logistic) framework for the repeat measures will be used (Halekoh, 2006; Yan J, 2004). The regression equation is presented below with Patient ID representing the random effect, and plasmapheresis method (study group) being fixed effect. Additional covariates are age, gender, BMI, and first-time donor status.

 $Logit(P(AE_{i,t}=1)) = \beta_0 + \beta_{Treatment} \times Treatment_i + \beta_{Age} \times Age_{i,t} + \beta_{Gender} \times Gender_i + \beta_{First \ Comer} \times First \ comer_{i,t} + \beta_{BMI} \times BMI_{i,t} + \varepsilon_{i,t},$

Corr(AE_{i,j}, AE_{i,k}) is exchangeable across all donors.

$$Corr(AE) = \begin{bmatrix} 1 & \gamma & \gamma & \gamma \\ \gamma & 1 & \gamma & \gamma \\ \gamma & \gamma & 1 & \gamma \\ \gamma & \gamma & \gamma & 1 \end{bmatrix}$$

Statistical Analysis Plan Version: 1.0 Date: 26-Apr-2020

AE represents the occurrence of a hypotensive AE (at least one), during the plasmapheresis procedure. *Treatment* is the variable representing plasmapheresis group (1=Experimental group, 0=Control group). For the *Gender* variable 1=Female, 0=Male. In *First comer* variable 1=First-time donor and 0=Repeat donor. First-time donors are those who have never undergone a plasmapheresis procedure. Age and BMI are continuous variables. i represents subject ID and t represents donation number for the given i subject.

Correlation structure within patients will be assumed to be exchangeable. Derivation of the final correlation model is currently in progress. The correlation structure can also be defined with the use of the historic data from the current study centers.

The above modeling will be used to obtain estimates of difference in proportions of significant hypotensive (vasovagal/hypovolemia) AE rates ($P_{Exper} - P_{Ctrl}$) in experimental and control groups along with its one-sided 97.5% upper limit of the CI calculated with Wald method.

[figure not shown]

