Survival analysis will be used to analyze the time-to-AE (significant hypotensive (vasovagal/hypovolemia)) data. Time to event is defined as time between the procedure start and the occurrence of the AE. Kaplan-Meier curves will be presented. Non-parametric Log-Rank tests will be conducted to evaluate differences between the two study groups. Survival modeling and hazard estimation will be used to obtain parameter estimates for the variables of interest. Other secondary objectives will be assessed with the use of continuous and discrete modeling techniques whenever applicable. Assessment and comparison of the relative rates will be conducted using repeat measure models and descriptive statistical techniques.

Statistical Analysis Plan Version: 1.0 Date: 26-Apr-2020

Effectiveness analysis will be conducted by comparing the distribution of collected plasma volumes across the two groups of the clinical trial.

Descriptive statistical summaries and advanced data visualization techniques will be used for data presentation.

Detailed description of the analysis related to the other secondary endpoints will be included in later versions of the SAP.

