3.4.2. SUBGROUP ANALYSIS DEFINED BY WEIGHT AND BMI

Information on Donors' weight will be collected prior to each donation. Three weight and three BMI groups will be defined.

- High weight group: Donors with weight more than 130lbs throughout the study;
- Low weight group: Donors with weight less or equal to 130lbs throughout the study;
- Borderline weight group: Donors who will have their weight group changed during the study (i.e. their weight will pass 130lbs threshold);
- High BMI group: Donors with BMI more than 30 throughout the study;
- Low BMI group: Donors with BMI less or equal to 30 throughout the study;
- Borderline BMI group: Donors who will have their BMI group changed during the study (i.e. their BMI will pass 30 threshold).

ClinStat Device

Statistical Analysis Plan Version: 1.0 Date: 26-Apr-2020

For low and high BMI and weight subgroups estimates of significant hypotensive (vasovagal/hypovolemia) AE incidence rates along with their 95% CIs will be reported separately per experimental and control arms. Estimation will be conducted using Agresti-Coull method (Agresti, 1998). Sensitivity analysis will be conducted using exact method based on a binomial distribution, and Wald method with or without continuity correction. If data allow, additional model based analysis will be performed with the approach outlined in the primary analysis section with introduction of additional categorical covariate representing weight (or BMI) subgroups. Data of the borderline groups will be analyzed separately as deemed appropriate.

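### Subgroup intervals over all donations treat donations as independent, and the log-rank test names no donor adjustment; repeat-donor results are overprecise if donors return after an event

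*SAP*

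**What the plan says.** The SAP recognises the clustering in its primary analysis (3.1.1): "Given the nature of the data where donors contribute multiple data samples (donations), Generalized Estimation Equations Logistic Regression" is the chosen framework.

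The subgroup sections do not carry this through. In SAP 3.4.1, Analysis two compares the arms within first-time and repeat donors "using the data from entire ITT dataset (i.e. all donation"), and for the rates and 95% intervals "Estimation will be conducted using Agresti-Coull method". Sections 3.4.2 (weight, BMI) and 3.4.3 (gender) name the same method. The fallback in all three is "Sensitivity analysis will be conducted using exact method based on a binomial distribution, and Wald method with or without continuity correction". Section 3.3 names Agresti-Coull for category 1.1 events and adds "Similar statistical analysis and visualizations will be performed for total AEs by a study arm".

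For time to event (3.2), "Time to event is defined as time between the procedure start and the occurrence of the AE", and "Non-parametric Log-Rank tests will be conducted to evaluate differences between the two study groups". No clustering, stratification or robust variance is mentioned.

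Several passages point towards models, but none commits to a donor-adjusted interval per arm and subgroup:

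- Sections 3.4.1 to 3.4.3 add a model-based analysis only where the data support it. In 3.4.1 and 3.4.3 it adds first-time status or gender to a model that already contains that variable. No arm-by-subgroup interaction is named, and 3.4.1 promises only the status coefficient and its interval.
- Section 3.2 says, generically, "Assessment and comparison of the relative rates will be conducted using repeat measure models and descriptive statistical techniques". It gives GEE rates per arm, not per subgroup, and leaves detail on other secondary endpoints to later SAP versions.
- Section 3.3 makes alternative interval methods optional.

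On donations after an event, Protocol 7.1 keeps enrolled subjects in for later donations, and Protocol 6.1.3 leaves safety withdrawal to the healthcare provider. SAP Appendix 2 assumes, for the simulation only, that a donor stops after an event.

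**The concern.** Agresti-Coull, exact binomial and Wald intervals all take the number of donations as the number of independent observations. If one donor can contribute several correlated events, the variance of the rate exceeds the binomial variance and all three intervals are too narrow. Because the sensitivity methods share the assumption, none of them would reveal the problem.

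These intervals are the named output for four secondary endpoints (weight, BMI, first-time status, gender) in a donor-safety trial, where readers will look to the upper bounds for reassurance. Repeat donors are the most exposed. They are about 85% of donors (1 − 0.146, from the first-comer share in SAP Appendix 2).

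The log-rank test is the only test named for the time-to-event endpoint. Time is measured within a procedure and the synopsis speaks of comparing procedures, so one record per donation is the natural reading. Without a donor adjustment, such a test can reject too often.

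**Working it through.** **The plan's own figure.** The SAP gives no precision figure for the subgroup intervals. Its power figure (SAP 5: above 85%, 12,000 donations per arm, rate and margin 0.0015) reproduces with independent donations: SE = √(2 × 0.0015 × 0.9985 / 12,000) = 0.0004996, and Φ(0.0015/0.0004996 − 1.96) = Φ(1.042) = 85.1%.

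**Inputs (SAP 5 and Appendix 2).** 3,000 donors per arm; first-time share 0.146, so 438 first-time and 2,562 repeat donors; donations per donor K Poisson(4) truncated to 1–24, mean 4.075; female share 0.357. Event rates: repeat women 0.002098; repeat men 0.003061 − 0.002581 = 0.00048; first-time women 0.01302 and first-time men 0.003061 at the first donation, then the repeat rates. Correlation is 0.1 between the first and other donations and 0.5 among the others. For a repeat donor, the first in-trial donation is not a first-ever donation, so 0.5 throughout is a second reading.

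**Design effect at a common rate, all donors continuing.** DEFF = 1 + E[sum of pair correlations over ordered pairs] / E[K].

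- 0.1/0.5: 1 + (0.1 × 6.149 + 0.5 × 10.149) / 4.075 = 2.396, where 6.149 = E[2(K−1)] and 10.149 = E[(K−1)(K−2)].
- 0.5 throughout: 1 + 0.5 × 16.299 / 4.075 = 3.00, where 16.299 = E[K(K−1)].
- Exchangeable 0.1 (assumed): 1.40. Exchangeable 0.05 (assumed): 1.20.

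The normal approximation to coverage, 2Φ(1.96/√DEFF) − 1, gives 79%, 74%, 90% and 93%.

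**Simulation.** Events are thresholded correlated normals, with 4,000 arms per case for coverage. The log-rank runs use one record per donation, equal hazards, rate 0.0015, 2,000 trials, experimental procedures 848/777 = 1.09 times as long (assumed proportional to volume) and a 15% duration CV (assumed).

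| Scenario | Repeat-donor coverage (DEFF) | Women | Log-rank false positives |
|---|---|---|---|
| 0.1/0.5, all continue | 81% (2.39) | 83% | 19.6% |
| 0.5 throughout, all continue | 76% (3.04) | 80% | – |
| 0.1/0.5, half stop (assumed) | 89% (1.89) | 91% | 15.4% |
| 0.5 throughout, half stop (assumed) | 85% (2.31) | 87% | – |
| Exchangeable 0.1, all continue | 91% (1.42) | – | 10.3% |
| All stop, as Appendix 2 assumes | 96% (1.03) | – | 5.5% |

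Other subgroups with all continuing (0.1/0.5, then 0.5 throughout where run): above 130 lbs 84%, 79%; BMI groups 87–88%, 81–82%; 130 lbs or less 95%, 93%; first-time donors 93%. With all stopping, coverage is 96–99% across subgroups.

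Runs with one pooled repeat-donor rate (0.357 × 0.002098 + 0.643 × 0.00048 = 0.00106) agree: 82% at 0.1/0.5, 75% at 0.5 throughout, 91% at 0.1, 93% at 0.05 and 95–97% with stopping. An unadjusted two-arm score test in those runs rejected 20%, 25%, 9%, 7% and 4–5% of the time.

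**Interval width for repeat donors.** The expected count is about 11 events in 10,440 donations (2,562 × 4.075 × 0.00106). Plain Agresti-Coull: centre (11 + 1.92)/(10,440 + 3.84) = 0.1237%, interval 0.056–0.191%. With events and n divided by 2.40 (4.58 in 4,350): centre 0.1494%, interval 0.035–0.264%.

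**The case against.** The strongest objection is that the low coverage figures split one set of assumptions. Appendix 2 gives the 0.1/0.5 correlations and also says donors stop after an event. Taken whole, those assumptions leave no defect. The documents do not say how often a donor returns after a significant hypotensive event, and the planned listing of withdrawal-triggering events implies some stopping. A correlation of 0.5 at these rates is also extreme: for a repeat woman, the chance of an event at another donation, given one, is 0.002098 + 0.5 × 0.9979 = 0.50. With milder inputs the problem shrinks: repeat-donor coverage is 93% at exchangeable 0.05, about 94.5% at 0.02 and 95% at 0.01 with all continuing, 94% at 0.1 with half stopping, and 95% at 0.5 with 90% stopping. Finally, the log-rank record unit is not stated, survival modeling is also planned, and Protocol 9.5 makes the subgroup results descriptive.

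All of this stands as a limit on size. Material undercoverage needs substantial correlation together with substantial continuation. It does not remove the gap: stopping is a simulation assumption with no matching rule in the protocol, and no analysis in the SAP commits to a donor-adjusted interval per arm and subgroup. The log-rank figures hold only if the test is run with one record per donation. For category 1.1 and total events the documents give neither rate nor correlation, so that part is unquantified.

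**Conclusion.** The concern holds, conditionally. If events are correlated within donor and donors donate again afterwards, the named intervals for all-donation subgroup rates are too narrow and an unadjusted per-donation log-rank test rejects too often. For repeat donors, a nominal 95% interval covers 76–81% at the SAP's planning correlations with everyone continuing, 85–89% if half stop, and 91% at an assumed exchangeable 0.1. If all donors stop after an event, the binomial methods are adequate.

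First-time donors and donors of 130 lbs or less lose little. The primary test, Analysis one (first donations only) and the per-arm GEE rates in SAP 3.2 are not affected, and no decision rule depends on these intervals. This should be corrected but does not threaten the trial's main conclusion. Confidence in its size is medium, because the true correlation and the return rate are unknown.

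**What to change.** For every all-donation rate, make the main interval donor-clustered. One workable form is Agresti-Coull or Wilson with events and n each divided by a design effect: donor-robust variance over binomial variance, floored at 1. Estimate it within the subgroup with both arms pooled where events permit (for example, at least 10); otherwise take it from all ITT donors and say that this can be conservative. GEE-based rates per arm and subgroup would be an alternative where they can be fitted. Keep plain Agresti-Coull for Analysis one.

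For time to event, state the record unit and use a Cox or score test with donor-clustered robust variance. In the simulations above, the clustered score test rejected 4.3%, 4.5%, 5.3% and 5.5% of the time in the four log-rank scenarios, in table order.

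State in the SAP whether the analysis expects donations after an event, and reconcile the Appendix 2 assumption with Protocol 7.1.

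The cost is SAP wording and a few lines of code. At whole-arm scale, as an illustration (18 events in 12,000 donations), the interval goes from 0.093–0.239% to 0.068–0.308% at design effect 2.40 (65% wider) and to 0.085–0.260% at 1.40 (21% wider). It is essentially unchanged if donors stop. The proposed interval covered 95–99% over eight subgroups and seven scenarios; it is conservative in small groups, at about 97–98% in first-time donors and 99% at 130 lbs or less.

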3.4.2. SUBGROUP ANALYSIS DEFINED BY WEIGHT AND BMI

Information on Donors' weight will be collected prior to each donation. Three weight and three BMI groups will be defined.

- High weight group: Donors with weight more than 130lbs throughout the study;
- Low weight group: Donors with weight less or equal to 130lbs throughout the study;
- Borderline weight group: Donors who will have their weight group changed during the study (i.e. their weight will pass 130lbs threshold);
- High BMI group: Donors with BMI more than 30 throughout the study;
- Low BMI group: Donors with BMI less or equal to 30 throughout the study;
- Borderline BMI group: Donors who will have their BMI group changed during the study (i.e. their BMI will pass 30 threshold).

ClinStat Device

Statistical Analysis Plan Version: 1.0 Date: 26-Apr-2020

For low and high BMI and weight subgroups estimates of significant hypotensive (vasovagal/hypovolemia) AE incidence rates along with their 95% CIs will be reported separately per experimental and control arms. Estimation will be conducted using Agresti-Coull method (Agresti, 1998). Sensitivity analysis will be conducted using exact method based on a binomial distribution, and Wald method with or without continuity correction. If data allow, additional model based analysis will be performed with the approach outlined in the primary analysis section with introduction of additional categorical covariate representing weight (or BMI) subgroups. Data of the borderline groups will be analyzed separately as deemed appropriate.

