3.4.3. SUBGROUP ANALYSIS DEFINED BY GENDER

For gender subgroups (Male vs Female), estimates of significant hypotensive (vasovagal/hypovolemia) AE incidence rates along with their 95% CIs will be reported separately per experimental and control arms. Estimation will be conducted using Agresti-Coull method (Agresti, 1998). Sensitivity analysis will be conducted using exact method based on a binomial distribution, and Wald method with or without continuity correction. If data allow, additional model based analysis will be performed with the approach outlined in the primary analysis section with introduction of additional categorical covariate representing gender subgroups.

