5. SAMPLE SIZE CONSIDERATIONS

In order to evaluate the operating characteristics of the study design and the analysis methodology, extensive Monte-Carlo simulation study was conducted. The experiment was designed with an objective to mimic the real study as closely as possible (with assumptions presented in Appendix 3). The historic data on significant hypotensive AE rates, study population demographics, first-time donor status etc. was analyzed to inform the simulation study.

This experiment evaluated the relationship between number of subjects, number of donations and the probability of rejecting the null hypothesis for the various assumptions of the true AE rates. Type I error was evaluated for multiple scenarios when the true AE rate of the experimental arm was unacceptably large: $P_{Exper} - P_{Ctrl} > \delta$

NI margin δ is set at level of 0.0015 (0.15%). For the power analysis, 5,000 simulations were conducted and power was calculated as follows:

$$Power = \frac{N(reject H_0)}{N_{sim}} * 100\%$$

Power is calculated for rejecting H_0 at significance level of 2.5% (using 97.5% one-sided CI for the AE rate difference).

Statistical Analysis Plan Version: 1.0 Date: 26-Apr-2020

Incidence rate of AE in the experimental group is assumed to be 0.0015 (0.15%). The total sample size of 6,000 subjects (3,000 per group) with an expectation of 24,000 total donations yields acceptable profile of power and type I error.

In the scenario when the experimental procedure is at least as safe as the standard one there is greater than 85% power to establish the NI.

Type I error is below 2% for the scenario when $P_{Exper} - P_{Ctrl} = 0.00175$ and is as low as ~ 1% for

 $P_{Exper} - P_{Ctrl} = 0.0020.$

Performance of the estimation method during the simulations in terms of statistical power for detecting difference in levels of significant AE incidence rate in experimental versus control groups, given the δ =0.0015, in various scenarios is presented below in Table 1.

Table 1: Performance of estimation method using 24,000 plasmapheresis procedures.

PExper – PCtrl	≤0	0.0005	0.00075	0.0010	0.0015	0.00175	0.0020
Power	>85%	68.4%	49.4%	28.5%	5.7%	1.9%	1.1%

Statistical Analysis Plan Version: 1.0 Date: 26-Apr-2020

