Appendix 2: Assumptions for Sample Size estimation

PATIENT ID

100,000 Pat_ID are generated starting from 1 to 100,000 (size of population).

GENDER

The variable *Gender* is generated using *Female ratio* = 0.357 as mean. *Gender* follows Binomial distribution:

Gender ~ B(0.357)

Where Gender = 1 for females, Gender = 0 for males.

WEIGHT

The variable Weight follows Truncated Normal distribution with the following parameters:

Maximum weight: $W_{max} = 400$ lbs

Minimum weight: $W_{min} = 110$ lbs

Average weight: $\mu_{Weight} = 211.2$ lbs

Standard deviation of weight $\sigma_{Weight} = 50.85$

The assumptions were used based on the clinical site historic information provided

byHaemonetics.

HEIGHT

Similar, the variable *Height* follows Truncated Normal distribution with the following parameters:

Maximum height: $H_{max} = 84$ inches

Minimum height: $H_{min} = 56$ inches

Average height: $\mu_{Height} = 68.76$ inches

Statistical Analysis Plan Version: 1.0 Date: 26-Apr-2020

Standard deviation of height $\sigma_{Height} = 3.86$

The assumptions were used based on the clinical site historic information provided by

Haemonetics.

BODY MASS INDEX (BMI)

BMI is calculated for each patient using the following formula:

$$BMI = \frac{Weight(lbs)}{Height^2 (in)} \times 703$$

AGE

The following proportions of donors are included in the age categories described in Table 1.

Table 1: Age distribution of patients.

Age	18-20	21-24	25-44	45-64	65+
Proportions	0.0669	0.1512	0.5235	0.2530	0.0054

When generating ages for the patients we assume that the ages of patients are distributed uniformly within the categories.

ARM

The variable *Method* is generated using *Experimental method ratio* = 0.5 as mean. *Method* follows Binomial distribution:

Method ~ B(0.5)

Where Method = 1 for experimental arm, Method = 0 for standard arm.

NUMBER OF DONATIONS PER PATIENT

Average number of donations per patient is assumed to be 4. Thus, the expected number of occurrences $\lambda = 4$. Number of donations follows Truncated Poisson distribution with the Protocol No: TP-CLN-100467(AB)

ClinStatDevice

Statistical Analysis Plan Version: 1.0 Date: 26-Apr-2020

following parameters: $\lambda = 4$, minimum number of donations equals 1, maximum equals 24, since FDA recommends that donors must not undergo plasmapheresis more frequently than once in a 2day (48 hours) period or twice in a 7-day period.

FIRST COMERS

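### In sparse subgroups, chiefly donors at or below 130 lbs, the Wald sensitivity intervals in SAP 3.4.1 to 3.4.3 are not valid 95% intervals (minor)

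*SAP*

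**What the plan says.** SAP 3.4.2 defines the group as "Low weight group: Donors with weight less or equal to 130lbs throughout the study" and says of the low and high weight and BMI groups that "AE incidence rates along with their 95% CIs will be reported separately per experimental and control arms". Agresti-Coull is the main interval. The sensitivity sentence reads: "Sensitivity analysis will be conducted using exact method based on a binomial distribution, and Wald method with or without continuity correction". SAP 3.4.1 (first-time status) and 3.4.3 (gender) carry the same sentence, ending "and Wald method with or without continuity correction".

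None of the three sections says what to do when a cell has no events or very few. SAP 3.4 cautions only about low power, adding: "This may occur when the proportion of the mentioned subgroup in the whole sample is small". That concerns detecting a difference. It does not address whether an interval formula works.

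The rate in donors at or below 130 lbs is a listed secondary endpoint (Protocol 5.2). Protocol 9.5 bases subgroup analysis on descriptive summaries.

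**The concern.** The Wald interval takes its width from the observed proportion. With no events the estimated variance is zero and the interval shrinks to a point at 0%. The continuity correction adds only 1/(2n). Neither result reflects what a few hundred donations can rule out.

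The low-weight group is where this is most likely to happen. It is also a group of interest: Protocol 2.2 describes donors of lowest weight and plasma volume as potentially at highest risk under the current nomogram. A sensitivity analysis is meant to test whether the main interval is robust. Here one row could show an upper limit of 0% or 0.13% beside a main limit above 1%, purely because of the formula, and at zero events the error always runs in the reassuring direction. The phrase offering Wald with or without the correction also leaves open which version will be reported.

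**Working it through.** **Inputs**
- SAP 5: "The total sample size of 6,000 subjects (3,000 per group) with an expectation of 24,000 total donations", so 12,000 donations per arm; event rate 0.15%; margin 0.15%; one-sided 2.5% level.
- SAP Appendix 2: weight truncated normal, mean 211.2, SD 50.85, limits 110 and 400 lbs; 35.7% female; 14.6% first-time donors; event rates 0.3831% (female) and 0.1145% (male); within-donor correlation 0.1 with the first donation and 0.5 between repeat donations.
- Assumed here: donation frequency does not depend on weight, and donations are independent except where stated.

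**Checks against the SAP's own figures**
- The truncated weight model has mean 214.05 lbs; Table 4 of Appendix 2 shows 213.79 and 214.11.
- An unpooled normal approximation with 12,000 donations per arm, 0.15% in both arms and the 0.15% margin gives 85.1% power; the SAP states more than 85%.

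**Size of the low-weight group**
- Share at or below 130 lbs = (0.0551 − 0.0233) / (0.9999 − 0.0233) = 3.26%.
- 12,000 × 0.0326 ≈ 392 donations per arm, from about 98 donors.
- Expected events: 392 × 0.0015 = 0.59 per arm.
- P(0) = 0.9985^392 = 55.5% in one arm; in at least one of two arms, 1 − (1 − 0.555)² = 80%.

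**Upper 95% limits at 0 of 392**

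| Method | Formula at zero events | Upper limit |
|---|---|---|
| Wald | 0 + 1.96·√0 | 0% |
| Wald, corrected | 1/(2 × 392) | 0.128% |
| Exact | 1 − 0.025^(1/392) | 0.937% |
| Agresti-Coull | add 1.92 events and 3.84 donations, then Wald | 1.17% (lower limit −0.20%) |

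If the subgroup is smaller or larger than inferred, the order Wald / corrected / exact becomes 0% / 0.21% / 1.53% at 240 donations and 0% / 0.08% / 0.61% at 600.

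**Coverage of the nominal 95% interval**

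Coverage is the sum of binomial probabilities over the counts whose interval contains the true rate. At 0.15%, Wald contains it for 1 to 4 events only, so coverage = 0.327 + 0.096 + 0.019 + 0.003 ≈ 44%. The exact interval contains it for 0 to 2 events: 0.555 + 0.327 + 0.096 = 97.8%.

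| True rate | Source | P(0) | P(1) | Wald, either form | Exact and Agresti-Coull |
|---|---|---|---|---|---|
| 0.15% | SAP 5 | 56% | 33% | 44% | 98% |
| 0.21% | 0.357 × 0.3831% + 0.643 × 0.1145% | 44% | 36% | 56% | 99% |
| 0.383% | SAP female rate | 22% | 33% | 78% | 98% |

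**Within-donor correlation**

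Under a beta-binomial approximation with a common correlation of 0.1 to 0.5, P(0) rises to 0.61–0.75 at a rate of 0.15% and to 0.28–0.47 at 0.383%.

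**Other subgroup cells, Wald without correction**
- Gender: females 4,284 × 0.003831 = 16.4 expected events per arm, males 7,716 × 0.001145 = 8.8; coverage about 93% in each.
- BMI groups at 0.15%: about 94%.
- First donation only, repeat donors (SAP 3.4.1): 3,000 × 0.854 = 2,562 donations per arm. At an illustrative rate of 0.12% that is 3.1 expected events and coverage of about 81%; the corrected form recovers to about 95%.

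**The case against.** The plan already reports sound limits. Agresti-Coull is the main method and the exact interval stands in the same sentence as Wald. At 0 of 392 the output would show 1.17% and 0.94% next to a plainly degenerate interval from 0 to 0. No decision in either document depends on the Wald row, and the subgroup size is inferred from a simulation model, not stated. All of this stands, and it is why the point is minor.

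A reader might infer more than the documents support:

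- **That a corrected Wald limit of 0.13% falls under the non-inferiority margin and so would look like proven safety.** The 0.15% margin in SAP 3.1.2 applies to the difference between arms. A single-arm limit cannot be set against it.
- **That zero is always the likeliest count.** It is at 0.15% and 0.21%. Under independence it stops being so above about 0.255% (1/392). At the SAP's female rate, one event is likelier (33% against 22%), although correlation pushes P(0) back up.
- **That Wald fails in every subgroup.** In the gender and BMI groups coverage is close to nominal.
- **That the replacements are fully valid.** They also treat repeat donations as independent. With a common correlation of 0.5, exact coverage at 0.15% falls to about 91%.

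**Conclusion.** The point holds as a minor one. In cells with few expected events, above all donors at or below 130 lbs, the Wald interval in either form is not a valid 95% interval, and at zero events its upper limit is too low by roughly 0.8 to 0.9 percentage points against the exact limit. The coverage shortfall persists over the SAP's own range of rates, from 44% to 78%. These figures rest on the Appendix 2 weight model, equal donation frequency across weights and independent donations. The requirement to stay at or below 130 lbs throughout moves some donors to the borderline group, which would make the cell smaller and the gap wider.

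What is at stake is one misleading or discordant sensitivity row in a descriptive secondary analysis. The main subgroup intervals and the primary non-inferiority conclusion are unaffected.

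**What to change.** - In SAP 3.4.1 to 3.4.3, remove Wald as a sensitivity interval, at minimum for the low-weight group and other cells with few events, such as the first-donation-only analysis. Removing it throughout is the simpler wording and loses nothing, since the exact method stays.
- Keep the exact interval, or use the Wilson score interval (upper limit 3.84/(392 + 3.84) = 0.97% at 0 of 392).
- Cut the Agresti-Coull lower limit at 0.
- Where an arm difference is shown in a sparse subgroup, a score interval such as Miettinen-Nurminen may be used; 0 of 392 in both arms gives about −0.97% to +0.97%.
- Add a note that all these intervals treat repeat donations by one donor as independent.

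The cost is one sentence in three sections and a procedure option, with no effect on conduct or data collection. The downside is wider sensitivity intervals in sparse subgroups.
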